4. STUDY POPULATION AND ENROLLMENT

4.1 Inclusion Criteria

1. Age greater than or equal to 18 years
2. Currently hospitalized or in an emergency department with anticipated hospitalization.
3. Symptoms of acute respiratory infection, defined as one or more of the following:
 - a. cough
 - b. Chills, or a fever (greater than 37.5° C or 99.5° F)
 - c. shortness of breath, operationalized as a patient having any of the following:
 - i. Subjective shortness of breath reported by a patient or surrogate.
 - ii. Tachypnea with respiratory rate greater than 22 breaths per minute.
 - iii. Hypoxemia, defined as SpO₂ less than 92% on room air, new receipt of supplemental oxygen to maintain SpO₂ greater than or equal to 92%, or increased supplemental oxygen to maintain SpO₂ greater than or equal to 92% for a patient on chronic oxygen therapy
4. Laboratory-confirmed SARS-CoV-2 infection within the past 14 days.

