10.5 Time to Recovery

Recovery is defined as reaching category 1, 2, or 3 on the seven-category COVID Ordinal Outcome Scale. A patient can reach category 1, 2, or 3 on the seven-category COVID Ordinal Outcome Scale either by (a) being discharged from the hospital or by (b) being liberated from supplemental oxygen for the final time during the index hospitalization. Time to recovery is defined as the time between randomization and the first of either hospital discharge or liberation from supplemental oxygen for the final time during the index hospitalization. Time to recovery is an “in-hospital outcome” and does not reflect information on receipt of supplemental oxygen, rehospitalization, or death after discharge from the index hospitalization.⁷

For a patient who is not receiving supplemental oxygen at the time of randomization, and who never receives supplemental oxygen during the index hospitalization, the time to recovery is 0.0 days. For a patient who receives supplemental oxygen at any time between randomization and discharge from the index hospitalization, but who is not receiving supplemental oxygen at the time of discharge from the index hospitalization, the time to recovery is the time from randomization to the time of final receipt of supplemental oxygen during the index hospitalization. For a patient who is receiving supplemental oxygen at the time of discharge from the index hospitalization, the time to recovery is the time from randomization to the time of discharge from the index hospitalization. Patients who remain hospitalized and receiving supplemental oxygen 28 days after randomization are not considered to have experienced recovery. All patients who die prior to discharge from the index hospitalization are not considered to have experienced recovery. Patients who do not experience recovery will be awarded a value for the outcome of time to recovery of 28.0 days.

10.6 COVID Ordinal Outcomes Scale on Study Day 3

This outcome is defined as clinical status 2 days after randomization (measured on Study Day 3) as assessed with the seven-category COVID Ordinal Outcome Scale, as described in the section on the Primary Outcome. Data on clinical status is collected from the electronic health record during the hospitalization. Patients discharge prior to Study Day 3 will have the Day 3 COVID Ordinal Outcome Scale coded as level 2 (not hospitalized with limitation in activity).

10.7 COVID Ordinal Outcomes Scale on Study Day 8

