For calculation of oxygen-free days, supplemental oxygen is defined as oxygen administered by nasal cannula, face mask, high-flow nasal cannula, non-invasive ventilation, or invasive ventilation. Positive airway pressure (CPAP, BiPAP) provided solely at night as treatment for sleep-disordered breathing (e.g. obstructive sleep apnea) is not considered supplemental oxygen. Oxygen-free days are calculated as the number of whole calendar days alive and not receiving supplemental oxygen between randomization and study day 29. Patients who die before Day 29 receive a value of 0. If a patient survives through study day 29 and never receives supplemental oxygen, the number of oxygen-free days is 28. If a patient receives supplemental oxygen and survives through study day 28, the number of oxygen free-days is calculated as 28 minus the number of calendar days from the first day on which the patient receives supplemental oxygen until the last day on which the patient receives supplemental oxygen. Days on which the patient does not receive supplemental oxygen that occur between days on which the patient receives supplemental oxygen do not count towards the number of oxygen free days. Data on oxygen use are censored at hospital discharge and the last observed status will be carried forward (“in-hospital outcome”). That is, if the patient is receiving supplemental oxygen at hospital discharge, the analysis assumes they continue to receive supplemental oxygen through Study Day 29. If the patient is not receiving supplemental oxygen at hospital discharge, the analysis assumes the patient continues not to receive supplemental oxygen through Study Day 29.

10.9.2 Ventilator-free days to Day 28

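### SAP 10.9.1 makes no allowance for chronic home oxygen, so a home-oxygen user who recovers and is discharged alive scores zero oxygen-free days, the same as a death

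*SAP*

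**What the plan says.** **Eligibility.** Protocol 4.1 accepts any of several respiratory symptoms. Under hypoxemia, criterion 3c.iii includes "increased supplemental oxygen to maintain SpO₂ greater than or equal to 92% for a patient on chronic oxygen therapy". The SAP's table of key features repeats the criterion. Such a patient could also enter on cough, chills or fever, or reported breathlessness. None of the eleven exclusions in Protocol 4.2 removes chronic oxygen users.

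**Endpoint.** In SAP 10.9.1, "supplemental oxygen is defined as oxygen administered by nasal cannula, face mask, high-flow nasal cannula, non-invasive ventilation, or invasive ventilation". The only exception is positive airway pressure "provided solely at night as treatment for sleep-disordered breathing (e.g. obstructive sleep apnea) is not considered supplemental oxygen". For a survivor who received oxygen, the score is "calculated as 28 minus the number of calendar days from the first day on which the patient receives supplemental oxygen until the last day" of receipt. Oxygen-free days inside that span are not credited. Data stop at discharge and the last status is carried forward: "if the patient is receiving supplemental oxygen at hospital discharge, the analysis assumes they continue to receive supplemental oxygen through Study Day 29". Death before Day 29 scores 0, and a survivor never on oxygen scores 28. The general rule in SAP 10.9 treats part of a day on support as a whole day.

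**Analysis.** Oxygen-free days is one of the secondary outcomes in SAP section 6, analysed as ordinal with a cumulative probability model and logit link.

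**The concern.** At entry, 3c.iii judges a chronic oxygen user's hypoxemia against that patient's own usual oxygen: only an increase counts. SAP 10.9.1 has no such reference point. Someone on oxygen all day before the illness is on support from Study Day 1, is still on support at discharge, and is carried forward as on support to Day 29. Neither quick nor complete recovery can lift the score above 0, and survival cannot separate it from a death.

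For these patients the endpoint records their pre-existing lung disease and not the course of COVID-19. In the analysis they form a block at the worst rank in both arms that treatment cannot move, which pulls the estimated odds ratio towards 1.

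**Working it through.** **1. Reproduce the plan's boundary values.** The rule is 28 minus the calendar days from first to last oxygen day, with death set to 0.
- Survivor never on oxygen: 28.
- Death before Day 29: 0.

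Both agree with SAP 10.9.1.

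**2. Apply the rule to a continuous home-oxygen user discharged alive on usual oxygen.** The first oxygen day is Day 1. The last, after carry-forward, is the end of the window.
- Day 1 to Day 28, both counted: 28 - 28 = 0.
- Day 1 to Day 29, one end excluded: 28 - 28 = 0.
- Day 1 to Day 29, both counted: 28 - 29 = -1.

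No floor is stated. I take 0 as the intended value. The -1 comes from a 29-day window set against a maximum of 28, a separate matter from chronic oxygen.

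**3. Worked case.** Flow is raised from Day 1, returns to the home level during Day 4, and the patient is discharged on Day 5 and alive at Day 29.
- As written: 0.
- Counting only oxygen above usual: Days 1 to 4 are support days, because the partial-day rule makes Day 4 a full one. 28 - 4 = 24.
- A patient without chronic oxygen whose last oxygen day was Day 4 also scores 28 - 4 = 24.

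**4. Dependence on the acute course.** With one day of raised flow, the alternative score is 28 - 1 = 27. With twenty days it is 28 - 20 = 8. As written, both score 0.

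**5. Illustrative dilution.** The documents give neither the share *q* of chronic oxygen users nor a control distribution for this endpoint, so both are assumed.
- Control arm: 20% or 35% at zero, the rest spread evenly over nine higher levels.
- Treated arm: odds ratio 0.73 at every cut. This is the plan's detectable effect for the primary outcome, borrowed here.
- Share *q* fixed at the worst level in both arms: p' = (1 - q)p + q at level zero.
- n = 1000, s = P(treated better) - P(treated worse), U = ns/4, V = (n/12)(1 - Σp̄³). The log odds ratio is U/V, inverted to the scale where below 1 is benefit.
- Power = Φ(|U/V|√V - z), with z = √(2 ln 7) = 1.973 (two-sided 0.0485). The likelihood-ratio threshold of 7 serves only as a yardstick.

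| q | Apparent OR (20% / 35% at zero) | Power (20% / 35% at zero) |
|---|---|---|
| 0 | 0.731 / 0.731 | 0.81 / 0.80 |
| 2% | 0.738 / 0.736 | 0.78 / 0.78 |
| 5% | 0.748 / 0.743 | 0.75 / 0.75 |
| 10% | 0.764 / 0.756 | 0.68 / 0.69 |

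The first row returns 0.731 and not 0.73 because U/V is a one-step approximation. Chronic users who die, or who stay above usual flow throughout, would score 0 under either rule. So *q* is the share displaced by the rule, which is smaller than the share on chronic oxygen.

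**The case against.** **It is partly a choice of outcome.** A patient on home oxygen is not literally oxygen-free, and ties between survivors and deaths are common in such composites. Someone on oxygen from Day 1 who leaves on newly prescribed oxygen also scores 0, as does a patient still in hospital at Day 29 for hospital-free days. This stands as context. The difference is that newly prescribed oxygen is a residue of the illness, whereas usual home oxygen is not.

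**The night-time positive-pressure exception proves little.** It may only stop that therapy being counted as non-invasive ventilation. A reader might infer that the SAP has adopted a general principle of discounting chronic therapy and then broken it. The text does not go that far. The exception shows where an allowance would sit, and the case for one rests on the scoring result itself.

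**Time to recovery is not broken in the same way.** A reader might extend the point to SAP 10.5. That section already handles discharge on oxygen, counting the patient as recovered on the discharge date, while an in-hospital death is given 28.0 days. It also defines recovery as reaching category 1, 2 or 3 of the 7-point scale. Redefining liberation from oxygen there while leaving the scale alone would make an inpatient on home flow both category 4 and recovered. This objection stands in full.

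**A rule may exist elsewhere.** Protocol 7.2 mentions a manual of operations and the data capture system, which are not available here. But Protocol section 6 assigns outcome definitions to the SAP, and the SAP has no such rule.

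**Conclusion.** The point holds for oxygen-free days. By the stated rule, a continuous home-oxygen user who recovers and is discharged alive scores 0, tied with death. In the worked case the gap is 24 days.

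The effect on the trial is limited. A reader might infer bias between arms, but randomization should balance these patients, so what is expected is misclassification and some loss of sensitivity. With 2% to 5% fixed at 0, an odds ratio of 0.73 appears as about 0.74 to 0.75 and illustrative power falls from about 0.80 to between 0.78 and 0.75. These figures rest on an assumed share, an assumed control distribution and a borrowed effect size.

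A reader might also infer damage to the primary outcome. The documents do not support that: after discharge the 7-point scale places a survivor in category 1 or 2 whatever the oxygen use. The mortality stopping rule and the assertion of efficacy do not use oxygen-free days. This is an inexpensive improvement to one secondary endpoint, not a threat to the trial's main conclusion.

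**What to change.** In SAP 10.9.1, beside the sentence on night-time positive airway pressure, add: *For patients on chronic oxygen therapy before this illness, oxygen at or below the usual home level does not count as supplemental oxygen for oxygen-free days; the same applies to status carried forward from discharge.* Limit the sentence to this endpoint, leaving SAP 10.5 and the 7-point scale as they are.

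Record three items for this subgroup: chronic oxygen before the illness, usual flow, and the last day above usual flow. If the increase began after Day 1, the first such day is needed too. Protocol 7.1 lists no specific field for home oxygen, and Protocol 7.2 lists first and final dates of oxygen receipt but not return to usual flow. The items should therefore be collected before data lock.

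The cost is one sentence and two or three extra data items for what is probably a small subgroup, taken from history or chart. Usual flow will sometimes be imprecise. While the section is open, state a floor of 0 or the intended counting window, so that the literal count cannot give -1.

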11.1 Acute kidney injury

Acute kidney injury is defined according to the creatinine criteria for stage 2 or greater acute kidney injury defined in the 2012 Kidney Disease: Improving Global Outcomes (KDIGO) Clinical Practice Guidelines.⁸ Patients who are on renal replacement therapy at the time of randomization will not be eligible for the acute kidney injury outcome. Patients who historically had received renal replacement therapy but were not on renal replacement therapy at the time of randomization are eligible for the acute kidney injury outcome. For determining acute kidney injury, the serum creatinine value closest to randomization will be used as the “baseline” creatinine and creatinine values collected clinically during the patient’s index hospitalization will be compared to this baseline. In this trial, urine output will not be used in the definition of acute kidney injury. A patient will be classified as meeting the stage 2 or greater acute kidney injury definition if he/she meets any of the following: (i) creatine value during the index hospitalization at least 2-times the baseline value; (ii) increase in creatinine by an absolute 0.3 mg/dl over baseline and to at least 4.0 mg/dl; initiation of renal replacement therapy.

11.2 Receipt of renal replacement therapy

Patients who are already on renal replacement therapy at the time of randomization will not be eligible for the renal replacement therapy outcome in this trial. Patients who historically had received renal replacement therapy but were not on renal replacement therapy at the time of randomization are eligible for the renal replacement therapy outcome. Patients who have initiation of renal replacement therapy between randomization and hospital discharge will be classified as meeting the renal replacement therapy outcome. Renal replacement therapy includes hemodialysis, peritoneal dialysis and hemofiltration techniques, including continuous veno-venous hemofiltration. Patients who historically had received renal replacement therapy but were not on renal replacement therapy at the time of randomization are eligible for the renal replacement therapy outcome.

11.3 Documented venous thromboembolic disease (DVT or PE)

Patients meet the venous thromboembolism disease outcome if they have a clinically diagnosed deep vein thrombosis (DVT) or pulmonary embolism (PE) between randomization and hospital discharge. The clinical diagnosis must be accompanied by imaging confirmation.

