5. STUDY INTERVENTIONS

5.1 Treatment of Study Participants

A summary of the trial's schedule of events is included in Appendix A.

Timing of study procedures is based on the time of initiation of the study product infusion, which is defined as "Time 0". Study Day 1 is defined as the calendar day of study product infusion. For patients who are randomized but do not receive study product, time of randomization will be considered "Time 0" and Study 1 will be the calendar day of randomization. For most patients, randomization and study product infusion will occur on the same day; in the event the study product is infused on a different calendar day than randomization, Study Day 1 is defined as the day on which study product is infused. "Baseline status" represents the patient's status immediately prior to study infusion, and baseline variables should represent information available before and as close as possible to initiation of the study infusion. The primary outcome will be assessed on Study Day 15 which corresponds to 2 weeks (14 days) after the receipt of the study infusion.

Transfusion of convalescent plasma or placebo will be administered as a single dose by clinical or research personnel while the patient is hospitalized and within 24 hours of randomization. Participants randomized to active treatment will receive 1 unit of convalescent plasma, which has a volume of 200-399 ml infused intravenously. Patients randomized to placebo will receive 250 ml of lactated Ringer's with multivitamin additives infused intravenously. The duration of infusion is recommended to be between approximately 1 hour and 3 hours (at the discretion of the provider), with the specific rate of infusion determined by the site investigator based on an assessment of how quickly the participant can safely receive the intravascular volume load.

Study personnel will monitor patients for adverse reactions to the transfusion while the patient is in the hospital for 72 hours following the infusion; that is transfusion adverse reaction monitoring will be continued until Study

Day 4. For patients who are discharged prior to Day 4, study personnel will obtain safety outcomes from the patient or surrogate via telephone follow-up scheduled at Day 8. Research personnel will also assess patients at Day 15 and Day 29; these assessments will be completed by phone if the patient has been discharged from the hospital.

Screening, consent, and baseline

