7.3 Assessments Following Hospital Discharge

7.3.1 Acute Care Follow-up

For participants discharged to home or a post-acute care facility (e.g., long term acute care facilities, skilled nursing facilities, or acute rehabilitation facilities) prior to the Day 8, Day 15 or Day 29 assessment, we will perform these assessments via telephone follow-up. The Day 8 call window will be Day 8 through 14. The Day 15 call window will be Day 15 through 22. The Day 29 call window will be Day 29 through 36. During these telephone calls, we will interview the patient, LAR, or facility staff to assess:

- Date of death (if applicable)
- ED visits and hospital readmissions after hospital discharge
- Location at the time of the call (home, long term acute care facility, skilled nursing facility, acute rehabilitation facility, hospital)
- Selected non-laboratory safety outcomes after hospital discharge
- COVID-19 7-point Ordinal Clinical Progression Outcomes Scale

The follow-up period for vital status (dead versus alive) is through Study Day 29. For most patients, we will establish vital status during the Study Day 29 visit (either in person for those who remain in the hospital or by phone for those who have been discharged). For patients who are not reached for the Study Day 29 visit, we will seek to establish vital status via phone calls, emails, and searches through medical records, obituaries, social media, and other sources.

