10.1.1 Potential risks of receiving convalescent plasma

One potential risk to receiving convalescent plasma is the possibility of developing antibody-mediated enhancement of infection (ADE). ADE can happen in the setting of viral and bacterial diseases and occurs when antibodies increase the severity of disease. ADE has been described in other types of coronaviruses, and it is also possible that antibodies to one type of coronavirus could enhance disease with another strain.⁴³ However, in the setting of MERS and the closely related SARS-CoV-1, evidence suggests that the use of convalescent plasma is safe.^{7,28,44} Anecdotal evidence of the use of convalescent plasma in COVID-19 also indicates that this is a safe treatment option.^{32,33} Another possible risk to receiving convalescent plasma is that the patient may mount a sub-optimal humoral immune response resulting in susceptibility to reinfection as has been seen with respiratory syncytial virus.⁴⁵ However, these concerns seem minor as compared to the possibility of limiting the duration and severity of disease, and avoiding interventions like mechanical ventilation, ARDS and sepsis. There are also risks associated with any transfusion of plasma including transmission of transfusion transmitted viruses (e.g. HIV, HBV, HCV, etc.), allergic transfusion reactions, anaphylaxis to transfusion, febrile transfusion reaction, transfusion related acute lung injury (TRALI), transfusion associated cardiac overload (TACO), and hemolysis should ABO incompatible plasma be administered. Another risk of plasma is thrombotic (clotting) complications, such as deep venous thrombosis, pulmonary embolism, myocardial infarction, and stroke. All study participants will be closely monitored for adverse events by study personnel.

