11.4 Documented cardiovascular event (myocardial infarction or ischemic stroke)

Patients meet the cardiovascular event outcome if they have a clinically diagnosed acute myocardial infarction or ischemic stroke between randomization and hospital discharge. A clinical diagnosis of acute myocardial infarction must be accompanied by elevation of the local cardiac troponin assay to greater than 3-times the upper limit of normal. A clinical diagnosis of acute ischemic stroke must be accompanied by imaging confirmation.

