11.6 Transfusion related acute lung injury (TRALI)

Patients meet the TRALI outcome if they have a clinically diagnosed TRALI between initiation of the study product and hospital discharge.

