11.7 Transfusion associated circulatory overload (TACO)

Patients meet the TACO outcome if they have a clinically diagnosed TACO between initiation of the study product and hospital discharge.

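### Thrombosis and MI/stroke are counted only to hospital discharge, so the arms are compared over unequal windows if discharge timing differs

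*SAP*

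**What the plan says.** Protocol 6 leaves outcome definitions to the SAP, so the SAP windows govern.

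- **Window.** SAP 11.3 requires a "clinically diagnosed deep vein thrombosis (DVT) or pulmonary embolism (PE) between randomization and hospital discharge", with imaging confirmation. SAP 11.4 requires a "clinically diagnosed acute myocardial infarction or ischemic stroke between randomization and hospital discharge", with troponin or imaging confirmation.
- **Why these events matter.** Protocol 10.1.1 states: "Another risk of plasma is thrombotic (clotting) complications, such as deep venous thrombosis, pulmonary embolism, myocardial infarction, and stroke".
- **Analysis.** Protocol 8.7 and SAP 7 give a risk difference without covariate adjustment. Neither mentions follow-up time or death as a competing event for these outcomes.
- **Post-discharge contacts.** Protocol 7.3.1 has calls at Days 8, 15 and 29 that cover "Selected non-laboratory safety outcomes after hospital discharge", ED visits and readmissions. Protocol 5.1 and Appendix A add new medical conditions at the same contacts. For patients discharged before Day 4, protocol 5.1 says "study personnel will obtain safety outcomes from the patient or surrogate via telephone follow-up scheduled at Day 8". The selected outcomes are never named, and the SAP has no analysis for safety data from these calls.
- **Adverse event reporting.** Appendix B.3 exempts DVT, PE, MI and ischemic stroke unless the event is judged related or of uncertain relationship. Protocol 12.3, Table 4, does not require unrelated serious events to be recorded once 72 hours have passed since infusion.
- **Mortality.** SAP 10.2 counts deaths in any location to 28 days.

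**The concern.** Discharge occurs after randomization and lies on the path the treatment is meant to change. Time to discharge is a secondary outcome (protocol 6.2), and the two best categories of the primary scale are out-of-hospital states. If one arm leaves hospital sooner, its patients are watched for clots, MI and stroke over a shorter period. A crude risk difference attributes the resulting shortfall in events to treatment.

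There is a second loss even when stays are equal. A nonfatal PE after discharge, more than 72 hours from infusion and judged unrelated by the site, is outside the outcome definition and exempt from adverse event reporting. The protocol grants that exemption because such outcomes are recorded systematically, but the SAP definition stops at discharge. At stake is the randomized comparison for a harm the protocol itself identifies.

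**Working it through.** The plan states no length of stay, no VTE or MI/stroke rate and no power for safety outcomes, so there is no plan figure to reproduce. The only document input below is 500 patients per arm (SAP 4). Stays, hazards, the 5% control risk and the 28-day horizon are assumptions.

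**1. Share of 28-day events after discharge on day L.** Constant hazard: 1 − L/28. Hazard with half-life h days: 1 − (1 − 2^(−L/h)) / (1 − 2^(−28/h)).

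| Hazard | L = 5 | 7 | 10 | 14 |
|---|---|---|---|---|
| Constant | 82% | 75% | 64% | 50% |
| Half-life 10 d | 66% | 55% | 42% | 28% |
| Half-life 7 d | 58% | 47% | 33% | 20% |
| Half-life 5 d | 49% | 37% | 23% | 13% |

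The range on this grid is 13% to 82%.

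**2. Unequal stays, no true effect.** Take exponential stays with mean m and a constant hazard. The share counted is m(1 − e^(−28/m))/28.

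- m = 8 (control): 8 × 0.9698/28 = 27.7%
- m = 7 (plasma): 7 × 0.9817/28 = 24.5%
- Apparent risk ratio: 24.5/27.7 = 0.89

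The plan reports a risk difference. At a 28-day risk of 5% in both arms, the counted risks are 5% × 0.277 = 1.39% and 5% × 0.245 = 1.23%. The spurious difference is −0.16 points. Its standard error at 500 per arm is √[(0.0139 × 0.9861 + 0.0123 × 0.9877)/500] ≈ 0.7 points. With means of 10 versus 8 days the ratio is 0.83 and the difference −0.29 points (1.68% versus 1.39%).

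If the hazard instead decays exponentially with a mean of 7 to 14 days, 38% to 60% of events are counted and the null ratio is 0.88 to 0.94. With fixed stays (control 5, 7 or 10 days) and plasma patients leaving 1 or 2 days earlier, the spurious difference is −0.2 to −0.8 points across the four hazards in step 1.

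**3. True harm.** Let the 28-day risks be 5% and 7.5%, a ratio of 1.5 and a difference of 2.5 points.

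- Full 28-day window: 2.5 points, power 37% at an assumed two-sided 0.05 level (the plan specifies no test).
- To discharge, equal fixed stays of 5 to 10 days: 0.4 to 1.9 points, power 10% to 29%.
- To discharge, plasma patients leaving 2 days earlier: −0.1 to +1.3 points, apparent ratio 0.90 to 1.34.
- Exponential means of 8 versus 7 days, constant hazard: 7.5% × 0.245 − 5% × 0.277 = 1.84% − 1.39% = 0.45 points, apparent ratio 1.33. With a mean of 8 days in both arms it would be 2.5 × 0.277 = 0.69 points.

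In the last case truncation removes 1.8 of the 2.5 points and the one-day difference a further 0.24. All signs in step 2 reverse if plasma patients stay longer.

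**The case against.** **In-hospital ascertainment is a legitimate choice.** These are documented outcomes that need imaging or troponin, which the index record supplies. Protocol 7.2 names MI, stroke and DVT/PE in its in-hospital section, consistent with the SAP. The post-discharge outcomes are only *selected* and unnamed, and the Day 8 sentence in protocol 5.1 follows on from transfusion-reaction monitoring. This stands: the documents do not contradict each other outright, and they do not show that the calls ask about thrombosis. It does not remove the dependence of the window on discharge, and readmissions and new medical conditions, which are collected, would flag most serious events for checking.

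**Not every later event is lost.** Related serious events are reportable whatever their timing, and deaths are counted to Day 29. This also stands. What is lost is the between-arm comparison of nonfatal events, and a randomized comparison should not hinge on each site's causality judgment.

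**The effect may be small.** A shift of 0.16 points is well inside the 0.7-point standard error. If sicker patients both stay longer and clot more, the share counted is higher than shown. Both remarks are fair.

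**Two stronger readings a reader might infer are not supported.** One is that most of the 28-day risk is missed: neither document gives a stay, a rate or a 28-day horizon for these outcomes, and the assumed range includes shares well below half. The other is that lung reactions are affected in the same way. The transfusion-reaction outcome in SAP 11.5, which includes desaturation and new infiltrates, has a fixed 6-hour window. SAP 11.6 and 11.7 count "clinically diagnosed TRALI between initiation of the study product and hospital discharge" and "clinically diagnosed TACO between initiation of the study product and hospital discharge", which covers the protocol's 72-hour monitoring except for patients who leave before Day 4.

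**Conclusion.** The concern holds for VTE and MI/ischemic stroke. Their window ends at an event that treatment may change, and the planned risk difference makes no allowance for it. The direction is conditional: toward apparent safety if plasma patients leave earlier, toward apparent harm if they leave later. Equal discharge timing would remove this distortion but not the loss of post-discharge events.

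The size cannot be fixed from the documents. The calculations assume event hazards independent of length of stay and ignore competing death. On that basis the distortion from a one-day difference in mean stay is modest on the planned scale, and dilution of a true difference is the larger effect. This is an analysis weakness worth correcting, not evidence that harm will be concealed.

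**What to change.** 1. In SAP 11.3 and 11.4, define the events from randomization through Study Day 29 in any location, using the Day 8, 15 and 29 contacts and the readmission data already collected.
2. Treat death as a competing event in that comparison.
3. State in protocol 7.3.1 that the selected post-discharge outcomes include DVT, PE, MI and ischemic stroke.
4. Confirm reported events from imaging or troponin records where available, and list unconfirmed events separately.
5. Keep the in-hospital count as a secondary display.

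The cost is SAP and protocol wording and record requests for the few reported events. If the call forms do not already ask about these events, they would need a line added. The downside is that some post-discharge events will remain unconfirmed.
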